4.2.2. Month 1 visit

Locator information will be updated.

Clinical evaluations and procedures will include a contraception assessment, counseling and provision if desired, HIV pre and post-test counseling, risk reduction counseling and condom provision. Blood will be collected. HIV testing will be conducted according to national algorithm. Plasma and DBS will be stored. Participants with positive HBsAg results will be referred for care and treatment of active infection.

Urine will be collected and urine pregnancy testing conducted. Social harms and SAEs will be assessed and participants will receive additional counseling and referrals related to their SAEs as necessary.

A prescription for two bottles of PrEP will be written, one bottle of PrEP will be dispensed if no contraindications, and women will be counseled per South African national guidelines.

4.2.3. Month 2 visit

Locator information will be updated. Blood will be collected for DBS. PrEP adherence will be assessed using DBS. One bottle of PrEP will be dispensed and women will be counseled per South African national guidelines.

4.2.4. Month 3 randomization visit

Women with high adherence (i.e., TVF-DP ≥ 500 fmol/punch based on Month 2 drug levels) who have not missed PrEP refills at Month 1 or 2 will be considered ‘responders’. Responders will move to quarterly visits and continue to be offered the adherence support they were randomized to at enrollment. Pharmacy refills will be verified using electronic pharmacy records.

‘Non-responders’ (i.e., TFV-DP < 500 fmol/punch or missed PrEP refill) will be randomized to a more intensive adherence support – continued monthly counseling visits or quarterly visits with counseling based on drug levels at months 3 and 6. Randomization will be conducted with a ratio of 1:1 between the two study arms. We will use envelopes in order to assign “non-responding” subjects to the second intervention. Envelopes will be prepared by study staff in Seattle and site staff in Johannesburg will open the envelopes in the specified order only when they are ready to randomize a “non-responding” participant.

All women will continue with the intervention they were assigned in their initial randomization (WhatsApp groups or two-way SMS) regardless of if they are classified as responders or non-responders. Additional month 3 visit procedures are included in section 4.2.5.

[figure not shown]
In the case of public health emergencies, study procedures that require in person visits may be delayed, including blood draws to determine secondary randomization. Therefore, secondary randomization may be conducted using blood drawn from visits occurring between months 1 and 3.

4.2.4.1. Intervention: Monthly counseling visits

Women who are randomized to continue monthly visits will have visits at months 4, 5, 7, and 8 that are focused on counseling. During these visits, women will receive SOC counseling that is tailored to identify problems impacting adherence, generate alternative solutions, make decisions about the alternatives, and collaboratively decide on a plan regarding how to implement the solutions. Additionally, they will have special issue counseling that explores their experiences with intimate partner violence, mental health issues such as depression and anxiety, and drug and alcohol use. Counselors will keep a progress note for each session. Counseling sessions may be audio-recorded to ensure fidelity to counseling messages and these audio-recordings will be reviewed by study team members in the U.S.. Women in this arm will have all procedures listed in 4.2.5 at their 3, 6, and 9month visits.

4.2.4.2. Intervention: Counseling based on drug levels at 3 and 6 months

Women who are randomized to counseling based on drug levels will move to quarterly visits and receive adherence counseling based on DBS levels collected 2 and 6 months after PrEP initiation. Adherence counseling will be provided in person or remotely, depending on pandemic conditions. The following thresholds and counseling messages will be used for drug level feedback counseling at these visits:

>500 fmol/punch

Key message: You are doing great! Keep up the good work and remember that taking one PrEP pill every day is needed for strong protection against HIV.

Between detectable to 499 fmol/punch

Key message: It looks like you are trying to take the PrEP medication, but are having some difficulties. Remember that taking one pill every day is needed for strong protection against HIV. How can we help you do even better?

No TFV-DP detected (confirm BLQ level)

Key message: It looks like you haven't been able to take the PrEP medication. Is PrEP something that you are still interested in? If yes, how can we help you?

4.2.5. Quarterly Follow-up Visits

Quarterly visits will occur at 3, 6, and 9 months for all participants in all arms.

At all quarterly follow-up visits, locator information will be updated with specific attention paid to phone number changes. Behavioral data will be collected including information about HIV and pregnancy risk perception, sexual behavior (number of partners, partner's HIV status, vaginal and anal sex with partners), depression, stigma, HIV prevention self-efficacy, sexual relationship power, transactional sex, intimate partner violence, self-esteem, trauma, and alcohol and drug use.

Clinical evaluations and procedures will include a contraception assessment, counseling, and provision if desired, HIV pre and post-test counseling, risk reduction counseling, and condom provision. Medical history including assessment for acute HIV, STI symptoms, and concomitant medications will be conducted. If indicated, a symptom-directed physical exam will be conducted. STI treatment will be administered per local standard of care based on test results, physical exam, or participant-reported symptoms. Social harms and SAEs will be assessed and participants will receive additional counseling and referrals related to their SAEs as necessary. Blood and urine will be collected. At the month 6 and study exit visit, a self-collected vaginal swab will be collected.

Sufficient PrEP will be dispensed to last until the following quarterly scheduled study visit. Participants randomized to monthly visits will be dispensed PrEP at those visits.

HIV testing will be conducted according to the national algorithm. Pregnancy testing will be conducted on urine. Plasma and DBS will be stored.

At month 6, serum creatinine testing will be conducted for creatinine clearance. At months 6 and study exit visit, STI testing will be conducted for trichomonas, chlamydia, gonorrhea and syphilis.

At month 9, we will offer participants the option of receiving drug level feedback counseling via a new urine POC assay to assess acceptability and feasibility of this approach. We will use drug level counseling messages previously described in section 1.2.1. Following the drug level feedback counseling, we will ask participants to answer a series of questions on their feelings about the urine POC test and to compare the acceptability of drug level feedback counseling based on the urine POC test versus DBS testing. This counselling will focus on participants continued interest in taking PrEP, and facilitate linkage to PrEP services for ongoing PrEP access following study exit.

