The basis for the use of drug level feedback is that women in VOICE qualitative interviews reported a desire for feedback about their adherence with directed counseling.¹⁵ HPTN 082 randomized Zimbabwean and South African young women to standard adherence support (counseling, two-way SMS, and adherence clubs) with or without drug level feedback based on TFV-DP levels in dried blood spots. There was no difference in adherence levels at six months by arm and, the cost and logistics of the DBS TFV-DP levels do not warrant use for PrEP adherence counseling. Notably, almost 40% of women in the drug level feedback arm across all study sites either did not receive counseling because DBS had to be batch-shipped and performed, and the results were not back at the next monthly visit, or did not receive the appropriate counseling message due to transcript errors in coding the laboratory results.⁷⁰ Although retrospective drug level feedback in addition to standard adherence support did not increase adherence at six months in HPTN 082 compared to standard adherence support, modifications to the DBS counseling approach to reduce laboratory shipment and testing delays and/or same day counseling using point of care tenofovir assays should be evaluated as potential improved strategies to support PrEP adherence. Point of care assays will be simpler to implement, easier to provide adherence messaging at the same encounter, and much less costly to implement than DBS assays which only two laboratories can perform. DBS-based adherence counseling may also be limited if participants have difficulty remembering their pill-taking behavior and adherence barriers from several months ago. In contrast, a recent US-based PrEP demonstration project found that drug-level feedback counseling using plasma tenofovir levels, which indicate a shorter period of PrEP use over the past week, significantly improved PrEP adherence among young men who have sex with men.⁶⁷ The shorter recall period about adherence behavior with the plasma tenofovir assay may explain these different findings, and a point of care assay would similarly provide an indicator of recent PrEP dosing and reduce participant burden to remember pill-taking over a longer period

of time. However, more research is needed on the acceptability and feasibility of using a point of care assay for drug level feedback counseling for PrEP participants.

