We will plan to use DBS levels to counsel participants at the months 3 and 6 visits. Although DLFB using DBS levels did not significantly impact PrEP adherence among AGYW in HPTN 082, the study team has learned critical lessons on how to manage the process to ensure sample collection, testing and reporting timelines are reduced and transcript errors in coding laboratory results and delivering the correct counseling message are minimised. Qualitative data from this study has also shown that DLFB via DBS was feasible and acceptable to young women. Importantly, we will be able to improve our DLFB counseling procedures using DBS from these key lessons learned in HPTN 082 and have the potential to answer questions about the impact of DBS DLFB counseling for AGYW when done with fewer transcription errors and in this stepped-up care approach. The DBS TFV-DP provides an objective measure of cumulative adherence in the prior 4-6 weeks, which is not susceptible to the ‘white coat effect’ of taking medication immediately prior to clinic. The threshold of 700 fmol/punch, which represented consistent dosing (≥ 4 times a week) and was associated with 100% efficacy in iPrEx,⁶⁸⁷ is being used for adherence counseling in HPTN 082. However, we will use a threshold of 500 fmol/punch at the 2-month study visit to more sensitively classify consistent dosing in this cohort. The thresholds and counseling about adherence based on drug level feedback at months 3 and 6 are depicted below. These thresholds and counseling messages were developed in consultation with Drs. [name] and [name].

>500 fmol/punch

Key message: You are doing great! Keep up the good work and remember that taking one PrEP pill every day is needed for strong protection against HIV.

Between detectable to 499 fmol/punch

Key message: It looks like you are trying to take the PrEP medication, but are having some difficulties. Remember that taking one pill every day is needed for strong protection against HIV. How can we help you do even better?

No TFV-DP detected (confirm BLQ level)

Key message: It looks like you haven't been able to take the PrEP medication. Is PrEP something that you are still interested in? If yes, how can we help you?

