We will also introduce a new point of care urine assay for drug level feedback counseling at the month 9 visit to assess acceptability and feasibility of this assay compared with using DBS for drug level feedback (DLFB). Such an assay was not available at the start of PrEP SMART enrollment, but has since become available. This point of care urine (POC) assay was recently developed to measure TFV levels in urine⁷⁰⁶⁹. A POC assay could support real-time adherence monitoring to provide drug level feedback about recent PrEP dosing in the week prior to the clinic appointment, however more work is needed to determine the acceptability and feasibility of a urine POC assay for drug-level feedback counseling, given the shorter adherence assessment window. The POC lateral flow assay has a threshold of 1500ng/mL consistent with dosing in the last 4-7 days based on a directly observed therapy study, is being developed in collaboration with Alere Diagnostics, and will cost approximately \$3.⁷²⁴ Approximately 2-3 minutes after 3-4 drops of urine are placed on the urine test strip, a “control” line should appear. An additional “tenofovir test line” will appear only if a participant has TFV levels <1500 ng/mL indicative of no recent PrEP dosing. This threshold will be used to provide drug-level feedback counseling at the month 9 visit as depicted below. We plan to assess acceptability and feasibility of this new POC assay by using it for additional drug level feedback counseling among all participants during their Month 9 visit. All participants receiving the urine POC assay will be subsequently asked about their perceptions of acceptability, feasibility, and satisfaction with the assay. The subset of participants that previously received DLFB counseling using DBS will also be asked to reflect on which DLFB counseling option they preferred (DBS versus urine). DLFB

counseling using the urine assay will also provide an opportunity to counsel all participants on opportunities to continue receiving PrEP through other mechanisms in South Africa after they are exited from the study. Counselors will engage participants in a discussion of HIV risk perception and link interested young women to further PrEP services. The counseling messages were developed in consultation with Drs. [name] and [name]:

Control line only (one line appears on test)

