2.3. Exploratory Objectives

The exploratory objectives of this study are:

- To assess HIV incidence, and to assess the association with detectable TFV-DP in PrEP users who acquire HIV infection during the study.
- To describe antiretroviral drug resistance among women who acquire HIV infection.
- To assess acceptability and feasibility of a urine point-of-care test for drug-level feedback counseling.

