A subset of up to 25 women will also be recruited to participate in serial qualitative interviews, to explore factors that influence women's decisions to use PrEP and adhere to PrEP and their satisfaction with their assigned intervention(s) after their Month 2, Month 6, and study exit visits. A subset of 10 key informants (e.g., PrEP program managers, health department officials) and 15 clinic staff members will also be recruited to participate in in-depth interviews to explore their perceptions of the PrEP SMART interventions and facilitators and barriers to future intervention scale-up.

At month 9, women will be offered the option of drug level feedback counseling via a new urine POC test, as available, to assess acceptability and feasibility of the urine test.

Finally, we will review SMS and WhatsApp message content to determine participant engagement with the interventions and identify key themes around PrEP use, HIV risk perceptions, and intervention satisfaction.

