6.2. Endpoints

6.2.1.Primary Endpoint

The primary outcome is dried blood spot drug concentrations above 700 fmol/punch at 9 months.

6.2.2.Secondary Endpoints

- TFV-DP concentrations above 700 fmol/punch at 2 months.
- TFV-DP concentrations at 2 and 9 months as a continuous measurement
- Correlates of PrEP adherence at 2 and 9 months, adjusted for study arm.
 - Covariate characteristics assessed at baseline and follow-up will include: Sociodemographic characteristics; partnership characteristics; partner's HIV status; sexual behaviors; HIV risk perception; HIV stigma; PrEP interest; self-efficacy; alcohol and drug use; gender-based violence (GBV); disclosure to peers, family members, teachers, and partner(s) about PrEP use and participation in the study, and level of engagement with the different intervention approaches (e.g., number of SMS messages sent, number of WhatsApp messages sent, satisfaction with intervention received).
- Proportion of young women who discontinue PrEP, timing of discontinuation, and factors associated with PrEP discontinuation.
- Frequency of responding to SMS and WhatsApp messages over follow-up, stratified by “responder” or “non-responder” status after Month 3; content of WhatsApp discussions over follow-up, stratified by “responder” or “non-responder” status after Month
- Qualitative factors that influence women's decisions to use and adhere to PrEP, acceptability of PrEP in the first 2 months after PrEP acceptance, and satisfaction/preferences for the randomized intervention(s) received.
- Qualitative perceptions of our intervention package and opinions on scalability of the interventions from clinic staff and key informants' perspectives.

6.2.3.Exploratory endpoints

- Incident HIV infections, and adherence prior to HIV seroconversion based on drug levels
- Genotypic resistance among incident HIV infections
- Acceptability and feasibility of a urine point-of-care test for drug-level feedback counseling, among the subset of women who accept drug level feedback counseling via a new urine POC assay at their month 9 exit visit.

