Appendix IA: Schedule of Study Visits and Procedures

	Enrollment	Month 1	Month 2	Month 3	Months 4, 5, 7, 8	Months 6 & 9/Exit
Administrative and Behavioral Evaluations/Procedures						
Informed Consent	X					
Collect/Update Locator information	X	X		X		X
Validate phone number and texting capacity	X	X		X		X
Collect demographic information	X					
Apply inclusion/exclusion criteria	X					
Behavioral data collection	X	X		X		X
Standard HIV risk reduction counseling and condom provision	X	X	X	X	X	X
Assess PrEP interest	X					
Study drug adherence assessment		X	X	X	X	X
Study drug supply	X	X	X	X	X	X
Randomization	X			[X]		
Adherence counseling and support	X	X	X	X	X	X
Clinical Evaluations/Procedures						
Acute HIV assessment	X	X		X		X
Medical history (including concomitant meds and STI symptoms)	X	X		X		X
Contraceptive assessment and associated counseling as appropriate	X	X		X		X
Symptom-directed physical exam	[X]	[X]		[X]		[X]
STI syndromic assessment and management	X	X		X		X
Blood collection	X	X	X	X		X
Participant vaginal swab collection for STI testing ¹	X					X
Urine collection	X	X		X		X
Laboratory Evaluations/Procedures						
HIV testing	X	X		X		X
Hepatitis B serology (HBVsAg)	X					
Serum creatinine (for creatinine clearance)	X					M6
Urine pregnancy testing	X	X		X		X
STI testing (TV, GC/CT, syphilis)	X					X
Drug level concentration ³			X	[X]		[M6]
Plasma storage	X	X		X		X
DBS storage	X	X		X		X

[] As indicated

¹ Participant collected vaginal swab samples will be used for TV, CT/GC testing; urine will be used if self-collected vaginal samples not acceptable.

²Drug level concentration will be conducted for all participants at M2 and for those randomized to receive drug level feedback at M3 and M6.

Appendix IB: Schedule of Study Visits and Procedures for Participants with Suspected or Confirmed HIV Infection

	Possible seroconversion (≥positive HIV rapid test)	Confirmatory Visit
Administrative Evaluations/Procedures		
Update locator information	X	X
Linkage to HIV care and associated counseling		X
Clinical Evaluations/Procedures		
Symptoms directed physical exam	X	
Stop PrEP	X	
Blood collection	X	
Urine collection	X	
Laboratory Evaluations/Procedures		
HIV EIA	X	
Pregnancy testing	X	
CD4 cell count testing	X	
Viral load testing	X	
Plasma storage for tenofovir levels	X	
DBS storage for TFV-DP levels	X	
Genotypic resistance testing	X

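### Exploratory month 9 urine test: the endpoint in 6.2.3 counts only women who accept the test, and 4.2.5 drops the limit in 1.2.1 on who compares urine with DBS feedback

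*Protocol*

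**What the plan says.** The objective, in Protocol section 2.3, reads "To assess acceptability and feasibility of a urine point-of-care test for drug-level feedback counseling", with no restriction on which women count. Section 3.1 makes the test optional and dependent on supply: "women will be offered the option of drug level feedback counseling via a new urine POC test, as available". Section 4.2.5 also presents it as an option. The endpoint in section 6.2.3 is then confined to acceptors, "among the subset of women who accept drug level feedback counseling via a new urine POC assay at their month 9 exit visit".

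Two places say who compares the urine test with dried blood spot (DBS) feedback. The drug level feedback text in section 1.2.1 has every woman who receives the urine assay rate it, and limits the preference question: "The subset of participants that previously received DLFB counseling using DBS will also be asked to reflect on which DLFB counseling option they preferred". Section 4.2.5, the visit procedure, has participants answer questions about the urine test and then asks them "to compare the acceptability of drug level feedback counseling based on the urine POC test versus DBS testing". It refers back to 1.2.1 for the counseling messages but does not repeat the limit.

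Under section 4.2.4.2, DBS feedback goes only to non-responders randomized to that arm. The SAP's exploratory objectives and its two exploratory analyses cover HIV incidence with TFV-DP detection, and drug resistance. The urine test does not appear.

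**The concern.** The main issue is the endpoint population. A woman who is offered the test and turns it down has given direct evidence on acceptability. A visit at which the test could not be offered is evidence on feasibility. The endpoint as defined records neither. High ratings from acceptors are compatible with wide uptake or with very little, and no other endpoint or SAP analysis tells the two apart.

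The second issue is narrower. A site that follows 4.2.5 alone would ask responders and women in the monthly counseling arm to compare urine feedback with a form of feedback they never had. Their answers would outnumber those of women who can compare.

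What is at stake is the conclusion about the urine test, which is exploratory and descriptive.

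**Working it through.** **Endpoint population.** Set side by side, the objective (2.3) has no denominator, the offer (3.1, 4.2.5) goes to women at month 9 when the test is available, and the endpoint (6.2.3) covers acceptors. Two groups are lost between offer and endpoint: women not offered the test and women who decline.

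The documents give no expected uptake, so the figures here are assumptions that only show how far the two quantities can part. Let *u* be uptake, *f* the share favourable among acceptors and *d* the share of decliners who would have been favourable.

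- Endpoint as written = *f*, whatever *u* is.
- Among all women offered = *u·f* + (1 − *u*)·*d*.

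With *f* = 80%:

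| Uptake | Endpoint as written | All offered, *d* = 0 | All offered, *d* = 1 |
|---|---|---|---|
| 50% | 80% | 0.5 × 0.8 = 40% | 0.40 + 0.50 = 90% |
| 70% | 80% | 0.7 × 0.8 = 56% | 0.56 + 0.30 = 86% |
| 90% | 80% | 0.9 × 0.8 = 72% | 0.72 + 0.10 = 82% |

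The true value of *d* is unknown, since a woman may decline for reasons unrelated to the test, such as lack of time. The gap between the last two columns is the size of what uptake and reasons for declining would clarify. If all 350 planned evaluable women were offered the test, each 10% who decline would remove 0.10 × 350 = 35 women from the endpoint.

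**Who can compare.** Inputs: 175 evaluable women per first-stage arm and the Table 2 response rates (section 6.3), and 1:1 second randomization (section 4.2.4).

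The plan's non-responder totals reproduce from 175 × (1 − WhatsApp rate) + 175 × (1 − SMS rate):

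- 65% and 40%: 61.25 + 105 = 166.25 (Table 2: 166)
- 60% and 40%: 70 + 105 = 175 (Table 2: 175)
- 55% and 40%: 78.75 + 105 = 183.75 (Table 2: 184)

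Half go to DBS feedback:

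| Non-responders | Assigned DBS feedback | Share of 350 | Not assigned |
|---|---|---|---|
| 166.25 | 83.1 | 24% | 266.9 (76%) |
| 175 | 87.5 | 25% | 262.5 (75%) |
| 183.75 | 91.9 | 26% | 258.1 (74%) |

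The wider range in the text of 6.3, 70 to 105 non-responders per initial group, gives 140 to 210 in total and 70 to 105 assigned. That is 20% to 30% of 350, leaving 70% to 80% without DBS feedback. All counts are before refusals and before any visit at which the test is unavailable.

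**The case against.** Only a woman who has used a test can rate it, so acceptors are the right denominator for experience ratings. That stands, and the endpoint is incomplete rather than wrong. It can also be said that the number of acceptors will be known, so acceptors over month 9 attendees could be tabulated with no change. That is partly right. But such a ratio mixes women who declined with women never offered the test, and the *as available* condition makes that distinction matter.

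On the comparison question, the protocol can be read as a whole. Section 1.2.1 states the limit, already in terms of feedback received, and 4.2.5 is a shorter restatement that does not say every participant compares. This largely stands: the point is an inconsistency between two sections, and the limit is not missing from the protocol. No document specifies an analysis that pools the two groups. The remaining risk is that staff work from the visit procedure. Refusals alone would not remove it. Even if every woman in the feedback arm accepted, uptake among the others would have to fall below 70/280 = 25% to 105/245 = 43% before they ceased to be the majority.

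Two stronger readings are tempting. The Appendix IA footnote, "for those randomized to receive drug level feedback at M3 and M6", might suggest that after month 2 only the feedback arm has drug levels measured. It does not, because month 9 DBS levels are the primary endpoint for all women (sections 6.1, 6.2.1 and 6.4.1). Only the *feedback* is confined to one arm.

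A reader might also carry over the earlier trial's delivery failures, "almost 40% of women in the drug level feedback arm across all study sites either did not receive counseling" or received the wrong message, to shrink the group able to compare. The documents do not support that as a forecast. Women given a wrong message still experienced DBS feedback, and section 1.2.1 says that "the study team has learned critical lessons on how to manage the process". The earlier experience shows only that assignment and receipt can differ.

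**Conclusion.** The point holds as a low-cost improvement to an exploratory item. Its main part is that 6.2.3 answers only part of the objective in 2.3, because refusal and non-availability lie outside the endpoint and the SAP does not bring them back. The size of that gap cannot be estimated from the documents, and the uptake figures above are illustrations.

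The minor part is that 4.2.5 conflicts with 1.2.1. If followed alone, it would put the comparison to about 74% to 76% of women with nothing to compare. That share assumes 350 women evaluable at month 9, the Table 2 response rates and an even second randomization. Missed refills also count as non-response and up to 500 women may be enrolled, so actual numbers may differ.

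A reader might infer that the trial's main adherence conclusions are affected. They are not: no primary or secondary endpoint, sample size or error rate changes.

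**What to change.** 1. In 6.2.3, keep the experience ratings among acceptors and add uptake, defined as women accepting divided by women offered the test at month 9. Report reasons for declining where given, and show the number not offered separately.
2. In 4.2.5, repeat the limit from 1.2.1. Put the comparison question only to women with recorded receipt of at least one DBS feedback session, and base the preference result on them. Other women rate the urine test alone.
3. In the SAP, add one descriptive exploratory analysis covering both.

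The cost is one line in 6.2.3, one clause in 4.2.5 and a short SAP entry. The site must log offers, refusals and delivered DBS feedback sessions. The preference result will rest on a smaller group, but that is the group 1.2.1 already sets, so no usable information is lost. If offers were not logged at visits already held, report acceptors over month 9 attendees for those visits and state that this ratio cannot separate refusal from non-availability.
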